5.2 Study Rationale

The study design meets the objectives of pharmacokinetic profile and food effect assessments and the evaluation of safety, tolerability and exposure profile resulting from single and multiple dose administration, required in Phase 1 studies. Part 2 will initially evaluate the safety of multiple doses in participants aged 18 – 55 years. Once safety is established, the study will evaluate dosing in healthy participants of either gender in the >55-80 year age range to match the approximate age range of the target PD population. A typical crossover design is adopted for the evaluation of food effect. The single and multiple ascending dose stages are randomized, double-blind, and placebo-controlled. The number of participants is based on standard practices of clinical pharmacology and clinical development.

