7.1.3 Part 2 (MAD)

Part 2 is the MAD part of the study. After assessing eligibility during the 4-week screening period, approximately 16 participants (with a minimum of 2 of each gender per dose level cohort) will be enrolled in 2 sequential cohorts. Eligible participants in each cohort will come to the clinical unit on the day before the first study drug administration (Day -1), for baseline assessments and to confirm eligibility and will stay in the clinical unit for 14 days (13 nights), from Day -1 until Day 13. Participants will return to the clinical unit for outpatient PK blood sample collections on Day 15 (72 hours post-last dose), and Day 16 (96 hours post-last dose) as well as an outpatient follow-up visit that will take place 7 days after receiving the last dose of study drug, on Day 19 (between Day 19 and Day 22).

Each cohort will include 8 participants, 6 participants will receive ATH-399A and 2 participants will receive placebo. Dose levels of ATH-399A will be based on data from Part 1 (Part 1a and 1b) and recommendation from the SRC. Additionally, [REDACTED]

[REDACTED]

[REDACTED]

[REDACTED]

From Day 1 to Day 12, participants will receive either ATH-399A or placebo once daily (QD) for a total of twelve (12) consecutive days. On Days 1 and 12, participants will fast for a minimum of 10 hours prior to dosing and 4 hours following dosing. From Days 2 to 11, participants will fast for a minimum of 2 hours prior to dosing and 2 hours following dosing.

Following completion of each dose level (both cohorts), an SRC will review the safety and tolerability data through the follow-up visit of a minimum of 6 evaluable participants. The SRC will also review PK data for up to 24 hours post-last dose in at least 6 evaluable participants in

order to make decisions whether to escalate to the next planned dose level, decrease the next dose level, repeat a dose level, or to not evaluate any additional dose. The time interval when escalating the dose from the first dosing of Cohort 1 of the MAD to the first dosing of Cohort 2 of the MAD will be approximately 3.5 weeks.

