Blood samples for PK will be collected pre-dose and at specified time points up to 96 hours post-Day 12 dose. Vital signs, ECG, telemetry, safety lab (including drug screen, cotinine, and alcohol breath test), C-SSRS, and physical and neurologic examinations will be performed at specified times. AEs will be recorded throughout the study. For details regarding the timing of specific procedures see [Table 3](#).

Additional Cohort: Following assessment of MAD dosing in participants, an additional cohort of approximately 8 participants will be evaluated at a dose level determined to be safe by the SRC. After assessing eligibility during the 4-week screening period, 8 participants (approximately equal numbers of males and females, with a minimum of 2 of each gender), aged >55-80 years, inclusive, will be enrolled. The study drug will be administered once daily (QD) in the fasted state for a total of twelve (12) consecutive days. On Days 1 and 12, participants will fast for a minimum of 10 hours prior to dosing and 4 hours following dosing. From Days 2 to 11, participants will fast for a minimum of 2 hours prior to dosing and 2 hours following dosing. Six participants will receive ATH-399A and 2 participants will receive placebo once daily (QD).

Eligible participants in this additional cohort will come to the clinical unit on the day before the first study drug administration (Day -1), for baseline assessments and to confirm eligibility and will stay in the clinical unit for 14 days (13 nights), from Day -1 until Day 13.

Blood samples for PK will be collected pre-dose and at specified time points up to 96 hours post-Day 12 dose. Vital signs, ECG, telemetry, safety lab (including drug screen, cotinine, and alcohol breath test), C-SSRS, and physical and neurologic examinations will be performed at specified times. Adverse events will be recorded throughout the study. Participants will return to the clinical unit for outpatient PK blood sample collections on Day 15 (72 hours post-last dose), and Day 16 (96 hours post-last dose) as well as an outpatient follow-up visit that will take place 7 days after receiving the last dose of study drug, on Day 19 (between Day 19 and Day 22). For details regarding the timing of specific procedures see [Table 3](#).

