asthma with no hospitalizations or recurrence in adulthood are permitted to enroll. For the additional cohort in Part 2, any of the above are acceptable where the condition is stable for >6 months and, in the opinion of the Investigator, it does not impact participant safety.

20. A clinically significant abnormality on physical examination, neurological examination, ECG, or laboratory evaluations at screening and Day -1.
21. A QT interval measurement corrected according to the Fridericia rule (QTcF) > 450 msec during controlled rest at screening and Day -1, or family history of long QT syndrome.
22. Any clinically significant abnormalities in rhythm, conduction, or morphology of the resting ECG and any abnormalities in the 12-lead ECG that, in the judgement of the Investigator or Medical Monitor, may interfere with the interpretation of QTc interval changes, including abnormal ST-T-wave morphology or left ventricular hypertrophy.
 - a) PR (PQ) interval shortening < 120 msec (PR < 120 msec but > 110 msec is acceptable if there is no evidence of ventricular pre-excitation).
 - b) PR (PQ) interval prolongation (>220 msec), intermittent second-degree (Wenckebach block while asleep or in deep rest is not exclusionary) or third-degree AV block.
 - c) Persistent or intermittent complete bundle branch block (BBB), incomplete bundle branch block (IBBB), or intraventricular conduction delay (IVCD) with QRS > 120 msec.

Note: at the Investigator's discretion, if an abnormal ECG is observed, the assessment may be repeated.
23. A clinically significant vital sign abnormality at screening or between screening and first dose administration. This includes, but is not limited to, the following in the supine position:
 - a) systolic blood pressure < 90 or > 140 mmHg,
 - b) diastolic blood pressure < 50 or > 90 mmHg, or
 - c) heart rate < 45 or > 100 beats per minute.
 - d) decrease in systolic blood pressure of 20 mmHg or higher, decrease in diastolic blood pressure of 10 mmHg or higher, or increase in heart rate of 30 bpm or higher within 2 to 3 minutes after passing from a supine to a standing position.

Note: at the Investigator's discretion, if a single abnormal vital sign is observed, the assessment may be repeated.
24. Significant (> 5%) weight loss or gain within 30 days prior to screening or between screening and first dose administration.
25. A history of seizures. Occurrence of a single febrile seizure is not exclusionary.

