9.11 Concomitant Therapy

Use of prescription or non-prescription drugs, herbal, and dietary supplements (including St. John's Wort) within 7 days (or 28 days if the drug is a potential hepatic enzyme inducer) or 5 half-lives (whichever is longer) prior to first dose administration and throughout the duration of study participation is prohibited for Part 1 of the study and Part 2 for participants aged 18-55 years, with the exception of paracetamol (acetaminophen) up to 2000 mg daily.

In Part 2 of the study, for the additional cohort of participants >55-80 years of age, the use of cholesterol medications, antihypertensives, hormone replacement therapy, asthma medications, thyroid medications, non-steroidal anti-inflammatory drugs, proton pump inhibitors, and antihistamines are permitted according to the medical judgement of the Investigator, as long as the participant is on a stable dose for at least 14 days prior to the first study drug dose. As needed, paracetamol up to 2000 mg per day is permitted.

Hormonal contraceptives may be allowed if deemed to not interact with the study drug PK.

Prune juice during mealtimes is allowed and will be provided by the clinic to treat constipation, if needed.

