12.5 Pharmacokinetic Analyses

Plasma and urine concentrations of ATH-399A will be tabulated descriptively by sampling time-point. Plasma pharmacokinetic parameters will be calculated by non-compartmental methods. Descriptive statistics (n, arithmetic mean, SD, minimum, median, maximum, coefficient of variation [CV], geometric mean and geometric CV) of the plasma PK parameters will be provided by part, dose, and cohort. Individual and mean plasma concentration-time profiles will be presented graphically on both linear and semi-logarithmic scales for each dose level using nominal time points.

For Part 1a, summary statistics will be used to describe the PK profile of [ATH-399A and metabolite(s), if applicable] for each dose level. The power model approach will be performed on AUC_{0-t} , AUC_{0-inf} , and C_{max} data to assess the dose-proportionality. An ANOVA will also be performed on the untransformed T_{max} , $t_{1/2 el}$, and λ_z data.

Part 1b (food effect) will be evaluated by analysis of variance, with terms for participant, sequence, period, treatment as fixed effects and participant within sequence as a random effect for the ATH-399A parameters C_{max} and AUC_{0-t} and AUC_{0-inf} . The exposure measurements (AUCs and C_{max}) will be log-transformed prior to analysis. The 90% CI for the ratio of population geometric means between test (fed) and reference products (fasting) will be provided for AUC_{0-t} and AUC_{0-inf} and C_{max} . Intra- and inter-subject CV will also be estimated.

For Part 2, summary statistics will be used to describe the PK profile of [ATH-399A and metabolite(s), if applicable] for each dose level. The power model approach will be performed on C_{max} , AUC_{0-tau} , $C_{max ss}$, $C_{min ss}$, AUC_{0-t} , and AUC_{0-inf} data to assess the dose-proportionality. An ANOVA will also be performed on the untransformed T_{max} , $T_{max ss}$, $t_{1/2 el}$, and λ_z data. Repeated measures analysis will be carried out on ln transformed pre-dose concentrations (Days 9 to 12) to determine attainment of steady-state. Comparisons between Day 1 and Day 12 PK parameters: AUC_{0-24} versus AUC_{0-t} , C_{max} versus $C_{max ss}$, and T_{max} versus $T_{max ss}$ will be done by ANOVA. Ratios (Day 12/Day 1) and 90% geometric CI will be computed for AUC and C_{max} .

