2.3.2 Secondary Objectives

- To assess the plasma PK of multiple doses of ATH-399A in up to 2 ascending dose groups in healthy male and female participants.

3. Study Description

This study will be a first-in-human evaluation of the safety and pharmacokinetics of single and multiple doses of ATH-399A in healthy adults in the 18-55 year age range, multiple doses in healthy participants in the >55-80 year age range, and will also evaluate the effect of food on ATH-399A safety, tolerability and PK. This is a randomized, Phase 1 three-part study. Part 1a is a placebo-controlled, double-blind, single ascending dose (SAD) safety, tolerability, and PK evaluation of ATH-399A. Part 1b is an open-label, single dose, food-effect, safety, tolerability, and PK evaluation of ATH-399A. Part 2 is a placebo-controlled, double-blind, multiple ascending dose (MAD) safety, tolerability, and PK evaluation of ATH-399A in 2 different age groups.

This document is confidential.

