8.3 Assessment of Dose Proportionality

For Part 1a, the power model approach will be performed on AUC_{0-t} , AUC_{0-inf} , and C_{max} data to assess the dose proportionality. For Part 2, the power model approach will be performed on C_{max} , AUC_{0-t} , $C_{max\ ss}$, $C_{min\ ss}$, AUC_{0-t} , and AUC_{0-inf} data to assess the dose proportionality.

The power model will include the PK parameter as the response variable and dose (mg) as the explanatory variable. For this model, the variable dose will be treated as a continuous variable. All treatments will be considered for the analysis (a minimum of three different treatments are required in order to conduct the analysis).

The form of the model is as follows:

PK Parameter = $e^\alpha \times Dose^\beta \times e^\epsilon$, where Dose ≥ 0 , and e^ϵ represents the associated error.

Thus, perfect dose proportionality is met when $\beta=1$ (ignoring error). This becomes a linear relationship following a natural-log transformation, to which a linear regression will be fit by ordinary least squares (OLS):

$\ln(\text{PK Parameter}) = \alpha + \beta \times \ln(\text{Dose}) + \epsilon$ where Dose > 0 , and ϵ represents the associated error.

This document is confidential.

The estimate of β together with a 90% confidence interval (CI) will be provided (for each PK parameter model), and this will be used to quantify dose proportionality. The following criterion may be used for exploratory dose proportionality evaluations: If the (two-sided) 90% CI for β is wholly contained within the interval, $[1+\ln(0.5)/\ln(\rho), 1+\ln(2)/\ln(\rho)]$, then dose proportionality is suggested across the investigated dose range.^a Here, ρ is defined as the ratio of the highest to lowest dose. This interval criterion will be reported along with the corresponding 90% CI estimate for β (presented to three decimal places).

The SAS code for the analysis model will follow the format below (using the Mixed Procedure to fit the linear regression). The input variables, datasets, and labels are depicted in italicized red text and have been given generic names.

```
proc mixed data=dataset order=data;
  model ln_pk_parameter = ln_dose / solution;
  estimate 'Beta Estimate' ln_dose 1 / cl alpha=0.1;
  ods output estimates =estimates;
run;
```

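### Part 2 power model: the third treatment it needs is the >55-80 year cohort, and with ln(dose) as the only term an age-group effect shifts beta

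*SAP*

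**What the plan says.** SAP 8.3 regresses the log PK parameter on ln(dose) for Part 1a and for Part 2, with no other term in the text or the code. On which data enter, it says: "All treatments will be considered for the analysis (a minimum of three different treatments are required in order to conduct the analysis". Beta and its 90% CI are reported for every parameter. The interval criterion based on rho is optional and labelled exploratory.

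For Part 2, Protocol 7.1.3 says "approximately 16 participants (with a minimum of 2 of each gender per dose level cohort) will be enrolled in 2 sequential cohorts", all aged 18-55. The objective in SAP 2.3.2 agrees: "To assess the plasma PK of multiple doses of ATH-399A in up to 2 ascending dose groups in healthy male and female participants". The only other planned cohort is the older one. Protocol 7.1.3 says "an additional cohort of approximately 8 participants will be evaluated at a dose level determined to be safe by the SRC", and Protocol 5.2 gives the order: "Once safety is established, the study will evaluate dosing in healthy participants of either gender in the >55-80 year age range". SAP 3.3.3 and 3.4 number it Cohort 3, and SAP 6.1 gives Part 2 three active labels, all with the dose to be determined.

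The older cohort has its own entry rules. Protocol 8.2, after listing excluded organ-system conditions, adds: "For the additional cohort in Part 2, any of the above are acceptable where the condition is stable for >6 months". Protocol 9.11 relaxes the medication ban: "for the additional cohort of participants >55-80 years of age, the use of cholesterol medications, antihypertensives" and several other chronic medicines are allowed on a stable dose. No age term, age-restricted fit or sensitivity analysis is given for dose proportionality.

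**The concern.** One cohort carries the whole age-group contrast as well as part of the dose contrast. If exposure at a given dose differs between the age groups, for whatever reason, a model with ln(dose) alone attributes part of that difference to dose. Beta and its CI would then be reported as a statement about dose proportionality although age group and dose are not separated.

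A second gap appears if the older cohort receives a dose already used in a younger one. SAP 8.3 does not say whether *different treatments* means dose levels or cohorts, and its plot description names both without choosing. Under the first meaning the model is not run; under the second it runs with the two effects mixed. The dose class variable in SAP 8.3-8.5 would also merge the age groups in that case, unless its values are cohort-specific labels.

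**Working it through.** **Count of treatments.** Aged 18-55: 16/8 = 2 cohorts. Aged >55-80: 8/8 = 1 cohort. The total of 3 matches SAP Table 3.3-2, and 40 + 12 + 16 + 8 = 76 matches the stated enrolment. Placebo cannot be the third treatment, because SAP 5.2 restricts the PK population to participants dosed with ATH-399A. Part 1a does not supply one either, because SAP 8.3 specifies the model by part. Without the older cohort there are 2 treatments, below the minimum of 3. An extra 18-55 cohort after a Safety Review Committee (SRC) decision is possible but not planned.

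**Shift in beta.** Let x = ln(dose), a = 1 for older participants and 0 otherwise, and r = older/younger exposure ratio at equal dose. If the truth is alpha + beta·x + ln(r)·a + error, the slope fitted without a has expectation beta + w·ln(r), where w = Σa(x − x̄)/Sxx. This w is zero only when the older cohort's ln(dose) equals the mean of the two younger ln(doses), that is, at their geometric mean.

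Worked case, younger doses d and 2d, older at 2d, 6 active each. With ln d set to 0, x = 0, 0.693, 0.693 and x̄ = 0.462. Sxx = 6(0.462² + 0.231² + 0.231²) = 1.92, and w = 6(0.231)/1.92 = 0.721. With ln 1.3 = 0.262 and ln 1.5 = 0.405, the shift is 0.721 × 0.262 = 0.19 or 0.721 × 0.405 = 0.29.

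**Illustrations.** Assumed, not in the documents: true beta 1, CV 30% (sigma = √ln(1.09) = 0.294), r = 1.3 or 1.5, and the dose patterns shown, which are not dose proposals. Coverage of the nominal 90% CI is simulated (18 participants, 16 df); with r = 1 it returns 90%.

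| Younger doses | Older dose | w | Shift, r = 1.3 / 1.5 | Coverage, r = 1.3 / 1.5 |
|---|---|---|---|---|
| d, 2d | 1.5d | 0.16 | +0.04 / +0.07 | 92% / 94% |
| d, 4d | 3d | 0.25 | +0.07 / +0.10 | 88% / 86% |
| d, 2d | geometric mean | 0 | 0 / 0 | 93% / 95% |
| d, 2d | 2d (repeat) | 0.72 | +0.19 / +0.29 | 81% / 72% |

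Coverage above 90% arises because the age effect also inflates the residual variance. A repeat of d instead of 2d gives the same shift with a negative sign.

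**Exploratory interval.** With rho = 2 it runs from 1 + ln(0.5)/ln 2 = 0 to 1 + ln 2/ln 2 = 2. In the repeat case the criterion is met 99.6% of the time with no age effect, and 97% (r = 1.3) or 90% (r = 1.5) with one. The pass/fail result therefore moves little; the distortion is in beta and its CI.

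**With an age-group term.** The shift is 0 and coverage returns to 90%. The half-width is t·sigma·√(slope variance factor):

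- d/2d/2d: 1.753 × 0.294 × √0.694 = 0.43 with the term (15 df), against 1.746 × 0.294 × √0.520 = 0.37 without it (16 df).
- d/4d/4d: 1.753 × 0.294 × √0.173 = 0.21, against 1.746 × 0.294 × √0.130 = 0.19.

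The unadjusted figures assume no age effect. In d/2d/2d with r = 1.5 the unadjusted half-width is itself about 0.43.

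**The case against.** **A repeated dose may stop the model.** SAP 8.3 asks for three *different* treatments and models dose in mg, and the Part 2 labels carry no age tag. Read as dose levels, a repeat leaves two treatments and no beta is produced. This stands: the +0.19 to +0.29 figures apply only if treatments are counted as cohorts.

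**The accumulation code in SAP 8.5 has three dose rows.** This suggests that the authors expected three distinct levels or cohort-specific labels. That is fair, so merging of age groups is a risk only if a dose is repeated and the class variable holds the mg value.

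**A higher older dose looks much worse.** With the older cohort at 4d, above younger doses of d and 2d, coverage falls to 58% (r = 1.3) or 29% (r = 1.5). A reader might take that as the likely damage. The documents do not support it: the older cohort follows the younger ones, at a level the SRC has judged safe. Part of the Part 2 dose-selection text is redacted, so the possible patterns cannot be settled here.

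**The SAP may seem to contradict the protocol.** Protocol 12.5 states no minimum and SAP 11 declares no changes. This is thin, because Protocol 12 says the SAP will add technical detail, and a minimum-data condition is such detail.

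**Adjustment costs precision.** By root mean squared error at CV 30%, the unadjusted fit is better when the age effect is small (d/2d/2d, r = 1.1: 0.222 against 0.244) and in d/2d/4d with r = 1.3 (0.225 against 0.245). In d/2d/2d with r = 1.3 the order reverses: √(0.189² + 0.294² × 0.520) = 0.284 against 0.294 × √0.694 = 0.245. The trade-off is real and is a reason to keep the unadjusted fit as supportive.

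**Reach.** Dose proportionality is not a listed endpoint, the study was not powered, PK is also summarised by dose and cohort, and Part 1a assesses proportionality separately over 5-80 mg in participants aged 18-55. All of this stands and limits the consequence.

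**Conclusion.** The point holds and the change should be made, but the consequence is modest. As planned, the three-treatment minimum can be met only with the >55-80 year cohort. When the model is fitted, an age-group effect on exposure shifts beta unless that cohort sits at the geometric mean of the two younger doses. The algebra needs no assumed effect size.

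The size does. It rests on undetermined doses, an assumed CV of 30% and assumed exposure ratios of 1.3 to 1.5. On those terms the shift is +0.04 to +0.10 with coverage of 86-94% in the two examples between the younger doses, and +0.19 to +0.29 with coverage of 81-72% for a repeat of the higher of two doses 2-fold apart, counted as cohorts.

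A reader might infer that the Part 2 proportionality result is bound to be wrong. The documents do not show that: no age effect is known, some dose patterns give little or no shift, and under one reading the model is not run at all. The primary safety objectives are untouched.

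**What to change.** In SAP 8.3, for Part 2:

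1. Add an age-group term (18-55, >55-80), i.e. `model ln_pk_parameter = ln_dose agegroup`, so that beta comes from the dose contrast within the 18-55 cohorts.
2. State that treatments are counted as cohorts (dose by age group) for the minimum, and that the model is not fitted if the 18-55 cohorts share one dose.
3. If the exploratory interval is reported, take rho from the 18-55 doses and note that two dose levels cannot check log-linearity.
4. Where SAP 8.3-8.5 use dose as a class variable, use cohort (dose by age group). This changes nothing if the doses are distinct and keeps the age groups apart if a dose is repeated.

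The unadjusted fit can be kept as a supportive result.

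The cost is one model term, one class variable and a few sentences, with no new data. Beta then rests on the 12 younger active participants, and the age term assumes equal residual variance in the two age groups. The loss of precision is small in the patterns worked above. The half-width doubles (0.21 to 0.43) only if the older cohort extends a d/2d range to 4d.

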Secondary	To assess the plasma PK of multiple doses of ATH-399A in 2 ascending dose groups in healthy male and female participants.
	Plasma PK parameters will include: 
• AUC_{0-t}• AUC_{0-inf}• C_{max}• C_{max, ss}• C_{min}• C_{avg}• T_{max}• T_{max, ss}• AUC_{0-t} (AUC₀₋₂₄, Day 12 dose)• AUC₀₋₂₄ (Day 1 dose)• λ_z• t_{½ el}• AR
AR=accumulation ratio; AUC=area under the curve; AUC _{0-t} = area under the curve for the defined dosing interval; C _{avg} = average plasma concentration; C _{max} = maximum plasma concentration; C _{min} = minimum plasma concentration; C-SSRS = Columbia Suicide Severity Rating Scale; ECG = electrocardiogram; λ _z = terminal elimination rate constant; PK = pharmacokinetics; t _{½ el} = terminal elimination half-life; T _{max} =time to maximum plasma concentration	
Study Design: This study is a randomized, Phase 1 three-part study: 
• Part 1a is a placebo-controlled, double-blind, single ascending dose (SAD) safety, tolerability, and PK evaluation of ATH-399A.• Part 1b is an open-label, single dose, food-effect, safety, tolerability, and PK evaluation of ATH-399A.• Part 2 is a placebo-controlled, double-blind, multiple ascending dose (MAD) safety, tolerability, and PK evaluation of ATH-399A, in 2 different age groups.	
Part 1a: (SAD) After assessing eligibility during a 4-week screening period, approximately 40 healthy participants will participate in Part 1a. Each eligible participant will be assigned to 1 of 5 cohorts (8 participants per cohort) to evaluate up to 5 single ascending dose levels. Proposed dose levels are: Cohort 1: 5 mg Cohort 2: 10 mg Cohort 3: 20 mg Cohort 4: 40 mg Cohort 5: 80 mg The starting dose will be 5 mg. Following completion of each dose level, a Safety Review Committee (SRC) will review the safety and tolerability data through the follow-up visit of a minimum of 6 evaluable participants. The SRC will also review PK data for up to 48 hours post-dose in at least 6 evaluable participants in order to make decisions whether to escalate to the next planned dose level, decrease the next dose level, repeat a dose level, or to not evaluate any additional dose. The determination of the highest dose level for this study will be based on	

emerging safety/tolerability and PK data, as recommended by the SRC, but will not exceed the maximum dose currently outlined in the protocol.

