3.2 Determination of Sample Size

The sample size for each stage was determined based on standard practice in Phase 1 food effect, SAD, and MAD studies empirically and was not powered for statistical significance. Cohort sizes were selected based on those commonly utilized in similar Phase 1 studies and thus generally considered sufficient to assess safety, tolerability, and estimate PK parameters.

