3.3 Treatment Assignment

3.3.1 Part 1a (SAD)

Participants allocated to the SAD part will receive a single dose of ATH-399A, or matching placebo, under fasting conditions. The planned dose levels and regimens are listed in Table 3.3-1, below.

Table 3.3-1: SAD Treatments

Cohort Number	Number of Participants Receiving ATH-399A	Number of Participants Receiving Placebo	Planned Dose
1	6 (1 sentinel, 5 non-sentinel)	2 (1 sentinel, 1 non-sentinel)	5 mg
2	6 (1 sentinel, 5 non-sentinel)	2 (1 sentinel, 1 non-sentinel)	10 mg
3	6 (1 sentinel, 5 non-sentinel)	2 (1 sentinel, 1 non-sentinel)	20 mg
4	6 (1 sentinel, 5 non-sentinel)	2 (1 sentinel, 1 non-sentinel)	40 mg
5	6 (1 sentinel, 5 non-sentinel)	2 (1 sentinel, 1 non-sentinel)	80 mg

For each dose level, 6 participants will receive ATH-399A and 2 participants will receive placebo. Each cohort will utilize sentinel dosing, with one participant receiving ATH-399A and one participant receiving placebo. For Cohorts 1-3, provided no clinically significant safety issues are noted in the 48 hours after dosing the initial 2 participants in the cohort, the 6 remaining participants in the cohort will be dosed. For Cohorts 4 and 5, provided no clinically significant safety issues are noted in the 96 hours after dosing the initial 2 participants in the cohort, the 6 remaining participants in the cohort will be dosed.

This document is confidential.

[figure not shown]
The SRC will consider the data on a cohort basis, but also on the basis of cumulative information across cohorts as the study progresses. All dose levels will be considered completed following SRC approval.

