The PK parameter values estimated from the power model will be plotted against dose. This plot will also include individual participant values and mean \pm SD (separately by treatment or dose level).

For Part 1a, an analysis of variance (ANOVA) will be performed on the untransformed T_{max} , $t_{1/2 el}$, and λ_z data. For Part 2, an ANOVA will also be performed on the untransformed T_{max} , $T_{max ss}$, $t_{1/2 el}$, and λ_z data. The SAS output for each model will be provided in listings.

The SAS code for the analysis model will follow the format below (using the Mixed Procedure to fit the linear regression). The input variables, datasets, and labels are depicted in italicized red text and have been given generic names.

```
proc mixed data=dataset order=data;
  class dose;
  model pk_parameter = dose;
  lsmeans dose;
  ods output estimates =estimates;
run;
```

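### SAP 8.3, Part 1a: the ANOVA on T_max, t1/2 el and lambda-z ignores the order of the five doses and yields no slope or CI, costing up to about 27 points of power against a steady trend

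*SAP*

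**What the plan says.** SAP 8.3 handles dose in two ways.

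- **AUC and C_max (power model).** "For this model, the variable dose will be treated as a continuous variable". The result is one slope on ln(dose) with a 90% CI, from an explicit ESTIMATE statement.
- **T_max, t1/2 el and lambda-z.** "For Part 1a, an analysis of variance (ANOVA) will be performed on the untransformed" values. The code lists dose in the CLASS statement, fits "model pk_parameter = dose" and requests LS means by dose. It has no CONTRAST, ESTIMATE or pairwise difference. It still carries the line that writes an ODS estimates table, which this model does not create. "The SAS output for each model will be provided in listings".

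Protocol 12.5 says only this much: "An ANOVA will also be performed on the untransformed" parameters. It does not say whether dose is ordered.

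Neither document gives an alpha level, hypothesis or decision rule for this ANOVA. SAP 3.2 says the sample size "was not powered for statistical significance".

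**The concern.** The Part 1a doses are ordered and each is double the one before. An overall F test on five classes returns the same value if the dose labels are shuffled, so it cannot use that order. The kinetic question is whether half-life, elimination rate or time to peak drifts with dose. A drift is a one-directional pattern, and a 1-df test is aimed at it.

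The reporting gap matters as much as the test. With 6 participants per dose and no powering, a reader of the study report needs the size of any drift and its uncertainty. The planned output gives five means and an overall p-value. A non-significant F could then be read as showing that half-life does not depend on dose, although the test had modest power to show otherwise.

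**Working it through.** **No document figure to reproduce.** The plan states no power, alpha, effect size or variability for this ANOVA.

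**Inputs from the documents**
- Doses of 5, 10, 20, 40 and 80 mg (Protocol synopsis; SAP Table 3.3-1).
- "For each dose level, 6 participants will receive ATH-399A and 2 participants will receive placebo" (SAP 3.3.1). So N = 5 × 6 = 30 active, with residual df = 30 − 5 = 25.

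**Assumptions (not in the documents)**
- Two-sided alpha 0.05.
- Lognormal t1/2 el with CV 20% to 50%.
- A change linear in ln(dose) from 5 to 80 mg.

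**Step 1: dose spacing.** Centred ln doses are (−2, −1, 0, 1, 2) × ln 2. Their sum of squares is 10 × 0.6931² = 4.805.

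**Step 2: noncentrality.** With slope b = ln(fold)/ln(16) and SD = √ln(1 + CV²), noncentrality = 6 × b² × 4.805 / SD². For CV 30% and a 1.5-fold rise:
- SD = √ln(1.09) = 0.2936
- b = 0.4055/2.7726 = 0.1462
- noncentrality = 6 × 0.02138 × 4.805 / 0.0862 = 7.15

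**Step 3: power.** For a log-linear trend both tests have the same noncentrality. The overall test uses F(4,25), critical value 2.76. The contrast uses F(1,25), critical value 4.24.

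| Rise, 5 to 80 mg | CV | Overall F | ln(dose) contrast | Loss (points) |
|---|---|---|---|---|
| 1.2-fold | 30% | 12% | 21% | 9 |
| 1.5-fold | 20% | 84% | 97% | 13 |
| 1.5-fold | 30% | 47% | 73% | 26 |
| 1.5-fold | 40% | 28% | 50% | 22 |
| 1.5-fold | 50% | 19% | 36% | 17 |
| 2-fold | 40% | 72% | 92% | 20 |
| 2-fold | 30% | 93% | 99% | 6 |

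**Step 4: range of the loss.** Over all trend sizes the loss runs from near 0 to a peak when trend power is about 73%. The peak is 26 points for the contrast on 25 df and 27 for a simple ln(dose) regression on 28 df. It is 20 or more only when trend power lies between about 44% and 92%, which is a 5-to-80 mg shift of about 0.96 to 1.79 SD. At 80% trend power (28 df) the F test has 54%. A 20,000-run simulation of that case gave 81% and 55%. At alpha 0.10 the maximum loss is about 24 points.

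**Step 5: other shapes.** The contrast's noncentrality is the overall one times the squared correlation of the pattern with ln(dose). At CV 30% and 1.5-fold:
- Rise in the top two doses only: 13.74 × 0.75 = 10.30, giving 78% (F) versus 87% (contrast).
- Rise at 80 mg only: 9.16 × 0.50 = 4.58, giving 58% versus 54%.

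For an umbrella shape the correlation is 0. At a noncentrality of 8.41, power is 54% for F and 5% for the contrast.

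**Step 6: scale.** Steps 2 to 5 work on the ln scale, but the SAP analyses untransformed values. A simulation of lognormal t1/2 el analysed untransformed (20,000 runs, 1.5-fold) gave 82% versus 97%, 44% versus 71%, 25% versus 47% and 16% versus 32% at CV 20%, 30%, 40% and 50%. Both tests rejected about 5% of the time with no trend.

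**Step 7: fewer dose levels.** With four doses reached, 80% trend power corresponds to about 60% for the F test. With three distinct levels, the most Part 2 can have, it is 67%. With two levels there is no loss.

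**The case against.** The strongest reply is that this is a valid, prespecified analysis of secondary parameters. The SAP does what Protocol 12.5 says, sets no decision rule and sends the output to listings. Dose means, and descriptive statistics by dose (SAP 8), would let a reader see an ordered pattern. Dose-dependent clearance, one cause of a changing half-life, is already examined through the AUC0-inf slope. All of this stands and limits the weight of the point. It does not supply a slope or interval for t1/2 el, lambda-z or T_max.

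A reader might go further and infer that a missed trend would mislead the Part 1b washout or the handling of Part 2 accumulation. The documents do not support that. SAP 1.2 places the final PK analysis after database lock, with no interim analysis. The washout may be adjusted on Part 1a PK data (Protocol 7.1.2), and escalation rests on Safety Review Committee review, not on this F test. Accumulation is estimated directly, with 90% CIs, in SAP 8.5.

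A reader might also infer a loss of 20 points or more against any steady trend. The table shows otherwise.

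One objection bears on the remedy. Cohorts 1 to 3 are sampled to 48 h and Cohorts 4 and 5 to 96 h (Protocol 7.1.1 and Table 6). Longer follow-up alone could lengthen the apparent half-life at 40 and 80 mg. The contrast has good power against a step in the top two doses, so it could pick up that artefact. This objection stands, and the slope needs a caveat.

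**Conclusion.** The point holds for Part 1a as a modest weakness. The ANOVA discards dose order, its only between-dose test is an overall F (4 and 25 df if all five doses are reached with 6 evaluable participants each), and it reports no slope or CI.

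Against a monotone trend roughly linear in ln(dose), the power loss relative to a 1-df contrast is up to about 27 points, and 20 or more only for moderate trends. The central illustration is 47% versus 73%, for t1/2 el at CV 30% and a 1.5-fold rise. Alpha, CV and effect size are assumptions. No power was computed for T_max, whose values cluster at the sampling times, so normal-theory figures would be only approximate for it.

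The consequence is confined to the report's exploratory statement on dose-dependence.

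**What to change.** In SAP 8.3, Part 1a, keep the class model, LS means and F test. Add alongside them a linear contrast in ln(dose):

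`estimate 'slope on ln(dose)' dose -2 -1 0 1 2 / cl alpha=0.1 divisor=6.931;`

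- **Divisor.** The slope is Σ(centred ln dose × mean)/Σ(centred ln dose)² = ln 2 × Σ(c × mean)/(10 × (ln 2)²), where c is −2 to 2. The divisor is therefore 10 × ln 2 = 6.931.
- **Reporting.** Give the slope per unit ln(dose) with its 90% CI, in the parameter's own units. The existing estimates output line then has a table to write.
- **Coding.** Sort the data by dose, because the code takes class order from the data. Recompute the coefficients and divisor from the actual ln(dose) values if a dose level is changed or not reached.
- **Caveat.** State that the trend in t1/2 el and lambda-z may reflect the longer sampling in Cohorts 4 and 5. A sensitivity estimate using samples to 48 h only in all cohorts would address this.

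The cost is a few lines of SAP text and code, with no new data or participants. It adds one exploratory result per parameter, plus the 48 h re-estimate if that is done. The contrast is weak for non-monotone shapes and slightly weaker if only the top dose differs, which is why the F test stays.
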